7.0 TREATMENT PLAN

7.1 Each cycle of CFZ therapy is given every 28 days. Up to 6 cycles of CFZ therapy will be administered on protocol. Four weekly doses of weekly rituximab, then 3 additional doses of monthly rituximab, will be administered to select patients who do not respond to CFZ following the first 2 cycles. (Total 7 doses of rituximab).

We anticipate accrual of 24 patients over 18 - 24 months. Accrual will be limited to the first 9 patients initially then paused -- if needed-- to ensure the stopping rule (section 12.2 and 12.3) has not been reached before additional patients are accrued.

Plasmapheresis may be undertaken at any point in the study when clinically indicated. If protocol therapy is discontinued for disease progression requiring other treatment, patients may go on to receive other therapy at the discretion of their physician, but will be removed from this study.

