7.2 Administration of Rituximab to CFZ Non-responders

Subjects who fail to achieve at least a 25% M-protein reduction based on SPEP m-protein quantification for WM, or partial response for MZL based on imaging, following 2 cycles of CFZ therapy will receive rituximab concurrent with CFZ.

7.2.1 Note: the bone marrow aspirate / biopsy after cycle 2 is exploratory and not to be used for response assessment or determination regarding rituximab.

7.2.2 IV Rituximab, pre-medications, and hypersensitivity management will be administered according to standard institutional or pharmacy guidelines.

| RITUXIMAB weekly x 4 doses (cycle 3) then monthly (cycles 4-6) | | | | |
|---|---|------|------|------|
| Treatment | Cycle 3-6 for patients not responding to CFZ (actual dates may vary +/- 3 days; cycle timing refers to CFZ) | | | |
| | C3 D1,8,15,22 | C4D1 | C5D1 | C6D1 |
| Rituximab 375 mg/m ² | X, X, X, X | X | X | X |

7.2.3 Following rituximab administration for WM, weekly laboratory evaluation of IgM levels (to evaluate for Ig M flare for clinical and study data purposes) is required. (See section 10, study calendar). As clinically indicated, viscosity measurement and other evaluation or management of hyper-viscosity syndrome, including plasmapheresis, should be undertaken. Weekly evaluation will continue until no longer clinically indicated.

7.3 Criteria for removal from protocol treatment: (Note: Subjects discontinued from CFZ will not receive rituximab on study.)

7.3.1 Symptomatic progression of disease after completion of at least 4 total cycles of CFZ therapy (with or without rituximab). IgM flare following rituximab (even if requiring plasmapheresis), or biochemical progression alone do not require removal from protocol treatment.

- 7.3.2 Inability to tolerate more than 20 mg/m² of CFZ during the first 4 doses of therapy, despite maximal supportive care.
- 7.3.3 Development of excess hematologic toxicity not responding to supportive care or persisting despite dose reductions—as outlined in Section 8.0
- 7.3.4 Development of any other unacceptable toxicities unless prophylactic measures can be taken for subsequent cycles.
- 7.3.5 Missed doses will not be replaced during a cycle. If a subject misses more than 2 doses of any cycle for reasons other than toxicity, the subject will be discontinued.
- 7.3.6 Delay of a treatment cycle for more than 4 weeks due to adverse events

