- 7.3.7 Completion of protocol treatment (maximum of 6 cycles, or 18 doses of CFZ).
- 7.3.8 The patient may withdraw from the treatment at any time for any reason.
- 7.3.9 Subjects may be removed from treatment in the event of study termination for any reason, as described under section 18.0.

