12.0 STATISTICAL CONSIDERATIONS

12.1 Accrual: We anticipate accrual of 24 patients over 18 - 24 months. Accrual will be limited to the first 9 patients initially then paused -- if needed-- to ensure the stopping rule (section 12.2 and 12.3) has not been reached before additional patients are accrued.

12.2 Sample Size: This is a Simon 2 stage (minimax) design with stopping for futility. The primary endpoint is overall response rate, measured after 2 cycles of therapy. This model requires 24 total patients to be assessable after 2 cycles.

The null hypothesis, that the true response rate of single agent CFZ is 25%, will be tested against a one-sided alternative. In the first stage, 9 subjects will be enrolled. If two or fewer patients responds, the study will be stopped for futility. If 3 or more respond, a total of 15 more subjects will be enrolled. The null hypothesis will be rejected if 10 or more responses are observed in 24 assessable subjects. This design yields a type I error rate of .05, and a power of 80%, when the true response rate after 6 cycles of CFZ is 50%.

Descriptive statistics will be used for baseline characteristics, and responses to treatment. Changes in mean fluorescence intensity pre- and post-CFZ of both CD20 and CD19 will be assessed compared using paired T testing.

Estimate time to best response, time to progression, and survival outcomes for subjects using Kaplan-Meier analysis.

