14.2 Adverse Events Reporting Procedures

All AEs (e.g., any new event or worsening in severity or frequency of a pre-existing condition or laboratory finding) with an onset date after the first dose of study drug must be promptly documented on the appropriate summary. Details of the event must include severity, relationship to study drug, duration, action taken, and outcome. Serious adverse events (SAEs) will be recorded on the appropriate form.

All AEs that are considered related to study drug must be followed to resolution or stabilization if improvement is not expected.

AEs should be reported from the time the subject receives their first dose of study drug, through 30 days post-last dose of study drug or initiation of a new anti-cancer therapy, whichever occurs first. In addition, the Investigator should report any AE that may occur after this time period that is believed to have a reasonable possibility of being associated with study drug. If a subject discontinues study prior to receiving any study drug, AEs must be reported through the end-of-study visit. AEs which completely resolve and then recur should be recorded as a new AE. For subjects who complete the end of study visit less than 30 days following their last dose of study drug, a follow up of ongoing AEs should be attempted by telephone, and documented in the subject's source. AEs continuing at 30 days post-last dose should have a comment in the source by the Investigator that the event has stabilized or is not expected to improve.

The Principal Investigator is responsible for evaluating all AEs, obtaining supporting documents, and determining that documentation of the event is adequate. Adverse events will be assigned a severity grade using the most current version of the NCI-CTCAE.

Grade 3 or higher AE's will be recorded, including laboratory abnormalities. Grade 1 and 2 abnormalities should only be recorded if they require treatment or are otherwise considered clinically significant by the Investigator.

The Principal Investigator may delegate reporting and AE assessment duties to Sub-investigators and must ensure that these Sub-investigators are qualified to perform these duties under the supervision of the Principal Investigator.

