14.3 Serious Adverse Events Definitions

An SAE is one that meets the following criteria:

- Death
- Life threatening experience defined as any adverse experience that places the subject, in the view of the Investigator, at immediate risk of death at the time of occurrence; i.e., it does not include a reaction that, had it occurred in a more severe form, might have caused death.
- Requires inpatient hospitalization or prolongation of an existing hospitalization (except scheduled hospitalizations for non-acute, unrelated cause such as an elective surgery)
- Results in persistent or significant disability/incapacity

- Is a congenital anomaly/birth defect in the offspring of an exposed subject
- Important medical events that may not result in death, be life-threatening, or require hospitalization, may be considered an SAE, when, based upon appropriate medical judgment, it jeopardizes the subject and may require medical or surgical intervention to prevent one of the outcomes listed in this definition.

Any death occurring within 30 days of the subject receiving study drug, regardless of the subject having discontinued from the study must be reported as an SAE.

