14.4 Serious Adverse Event Reporting and Documentation Requirements

All SAEs occurring from the time that the subject signs consent for study participation through 30 days after the last administered dose of study drug will be reported. All SAEs regardless of relationship to study drug must be followed to resolution or to stabilization if improvement or resolution is not expected.

If a subject is permanently withdrawn from the study because of a SAE, this information must be included in the initial or follow-up SAE report as well as the appropriate form for Study Discontinuation.

The Investigator is also responsible for notifying the Institutional Review Board (IRB) in accordance with local regulations, of all SAEs.

Additionally, the Investigator is responsible for reporting adverse events to Amgen and NCCN as described below:

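### Two secondary time-to-event estimates can be biased: deaths after removal from the study for progression are captured only by safety reporting, and the WM progression wording has no rituximab-flare exception

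*Combined protocol and SAP*

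**What the plan says.** Objective 1.2.2 names survival and time-related response measures as secondary objectives. Section 12.2 gives the whole analysis in one sentence: "Estimate time to best response, time to progression, and survival outcomes for subjects using Kaplan-Meier analysis". No event definition or censoring rule follows.

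**Removal.** Section 7.1 sets the condition "If protocol therapy is discontinued for disease progression requiring other treatment" and the consequence: "patients may go on to receive other therapy at the discretion of their physician, but will be removed from this study". Section 7.3, by contrast, lists reasons for leaving protocol treatment. They include "Symptomatic progression of disease after completion of at least 4 total cycles of CFZ therapy (with or without rituximab" (7.3.1) and "Completion of protocol treatment (maximum of 6 cycles, or 18 doses of CFZ" (7.3.7).

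**Follow-up.** The study calendar (section 10.0, footnote 8) describes standard-of-care visits up to one year from first dose. It has no vital-status item and says nothing about patients already removed.

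**Deaths seen through safety reporting.** Section 14.3 requires reporting of "Any death occurring within 30 days of the subject receiving study drug", even if the patient has left the study. Under 14.4, "All SAEs regardless of relationship to study drug must be followed to resolution or to stabilization". Under 14.2, "the Investigator should report any AE that may occur after this time period" if it is thought possibly related to study drug.

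**WM progression.** Appendix 20.2 defines progressive disease (PD) as a rise of 25% or more from nadir, to be confirmed, and/or clinical progression. Its footnote makes SPEP the primary measure. It gives no confirmation interval and does not mention flare. Section 13.2 describes a transient IgM flare after rituximab, 7.2.3 collects weekly IgM to detect it, and 11.0 assigns it a separate assay (nephelometry). Section 7.3.1 says that flare does not require removal from protocol treatment.

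**The concern.** Kaplan-Meier estimation assumes that censored patients have the same later risk as those who stay under observation. Patients taken off study because their disease progressed and needs other therapy are likely to be at higher risk of death. Censoring them near that point removes future deaths selectively, and the survival curve sits too high. Deaths that are never collected cannot be recovered at the analysis stage.

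The flare gap works in the other direction on a different endpoint. If a transient rise after rituximab is counted as PD, time to progression in rituximab-treated WM patients is too short. Two analysts could also date progression differently from the same laboratory values.

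The primary endpoint is response after two cycles. It is assessed before rituximab starts in cycle 3 and needs no survival follow-up.

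**Working it through.** The plan gives no figure for these endpoints, so there is none to reproduce.

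**1. Survival**

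Inputs from the documents: 24 patients (12.2); at most six 28-day cycles (7.1, 7.3.7), so the removal window is w = 168 days = 5.52 months; one year of follow-up (section 10.0), so survival is evaluated at 12 months.

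Assumed inputs, because the documents give no rates: constant monthly hazards of progression (l), of death before progression (m0 = 0.002) and of death after progression (m1). Let a = l + m0.

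- True survival: S(t) = exp(-a·t) + l·[exp(-m1·t) - exp(-a·t)]/(a - m1), at t = 12.
- Kaplan-Meier if every patient progressing within w is censored at progression: exp(-m0·w) × S(12 - w).
- Patients removed, of 24: 24·(l/a)·[1 - exp(-a·w)].
- Unseen deaths by month 12, of 24: 24 times the integral from 0 to w of l·exp(-a·s)·[1 - exp(-m1·(12 - s))] ds.

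Middle case (l = 0.03, m1 = 0.02, a = 0.032): S(12) = 0.6811 + 2.5 × (0.7866 - 0.6811) = 0.945. Kaplan-Meier = 0.9890 × 0.9770 = 0.966.

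| Case | l, m1 | True | Kaplan-Meier | Bias (points) | Removed | Unseen / all deaths |
|---|---|---|---|---|---|---|
| Low | 0.01, 0.005 | 97.43% | 97.57% | 0.1 | 1.3 | 0.06 / 0.6 |
| Middle | 0.03, 0.02 | 94.5% | 96.6% | 2.1 | 3.6 | 0.6 / 1.3 |
| High | 0.05, 0.05 | 86.1% | 93.6% | 7.5 | 5.8 | 2.1 / 3.3 |

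A simulation of 3,000,000 patients per case gives the same biases. Each is a ceiling for its case, because 7.1 removes only progressors who need other treatment. Simulated variants (low, middle, high):

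- Deaths captured for one further month after progression, close to the 30-day rule: 0.1, 1.9, 6.3 points.
- Progressors during cycles 1 to 4 stay until 112 days (3.68 months), and all on-therapy progressors are then censored: 0.1, 1.8, 6.2 points.
- Only patients first progressing between 112 and 168 days are censored: about 0.04, 0.5, 1.5 points.

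Standard errors at n = 24: sqrt(0.945 × 0.055/24) = 4.7 points for the middle case and sqrt(0.861 × 0.139/24) = 7.1 points for the high case. The middle bias is under half a standard error and the high one is about one.

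The ceiling depends on the assumed rates. A different set (2% 12-month death risk without progression, 10 to 30% progressing within six months, 50 to 90% 12-month survival after progression) gives about 1 to 12 points. That set lets nobody progress after therapy ends, which fits poorly with incurable disease, so it is not used for the size here.

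**2. WM time to progression**

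- Rituximab runs from cycle 3 day 1 to cycle 6 day 1 (7.2). SPEP is drawn on day 1 of each cycle (section 10.0).
- A flare present at cycle 4 day 1 and again at cycle 5 day 1 gives two SPEP values 28 days apart. If both are 25% or more above nadir, the 20.2 wording is met.
- The exemption in 7.3.1 concerns treatment and does not reach the endpoint definition.
- The documents give no flare rate or duration, so the number of false events cannot be derived. Each one is 1/24 = 4.2 points of the crude progression proportion.

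**The case against.** **Survival may not mean overall survival.** Section 12.2 says only survival outcomes. If progression-free survival is intended, progression is itself the event and the removal problem largely disappears, although the flare gap would then affect that endpoint. This stands: the survival bias is conditional on overall survival being estimated.

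**Later deaths might be used anyway.** Section 16.0 provides for authorized access to medical records, and no passage forbids using a known later death. A reader might go further and infer that no death after removal is ever recorded. That is wrong, since sections 14.2 to 14.4 capture some. But none of this is planned collection of vital status to one year.

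**The size is easily overstated.** A reader might infer that reported survival will be several points too high. The documents do not support this. They give no rates, 7.1 reaches only on-therapy progression needing other treatment, and 7.3.1 says that biochemical progression alone does not require removal from protocol treatment. The high case also assumes about 55% survival 12 months after progression, which sits uneasily with the protracted natural history described in 2.1.

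**Flare is partly handled.** Weekly IgM is a nephelometry measure, while PD rests on SPEP, so weekly flare values are not automatically PD. Confirmation on the scheduled SPEP takes about 28 days, which would screen out short flares. Sections 4.0 and 11.0 also rely on an International Workshop guideline that cannot be consulted here. These points reduce the risk, but the protocol's own PD wording remains silent on flare.

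**Labelling.** A reader might also conclude that the curves should be relabelled because some patients receive rituximab. The title and section 2.2 already describe a response-adapted strategy, so no change is needed.

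**Conclusion.** The point holds for secondary endpoints only.

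For survival, following 7.1 as written tends to bias overall survival upward, provided that overall survival is what 12.2 intends, that removed patients are censored at or soon after progression, and that progression raises the risk of death. Under the three assumed scenarios the 12-month overstatement lies between about 0 and a ceiling of 7.5 points, at most about one standard error with 24 patients. These figures illustrate the mechanism and do not predict the result.

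For WM time to progression, the wording of 20.2 allows a confirmed rituximab flare to count as PD. The direction is toward shorter time to progression; the frequency is unknown.

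Neither gap touches the primary response rate or the futility rule. Both merit correction because the remedy is cheap and uncollected vital status cannot be restored later.

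**What to change.** **Survival.**

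- Reword 7.1 so that these patients leave protocol treatment but stay in study follow-up. Who stops treatment does not change.
- Collect vital status by record review for every patient to the existing limit of one year from cycle 1 day 1, unless consent to data collection is withdrawn.
- Define overall survival in 12.2 as cycle 1 day 1 to death from any cause, censored at the date last known alive.

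**WM progression, for the endpoint analysis only.**

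- A biochemical rise first seen during rituximab treatment, without clinical progression, counts as PD only if it persists on SPEP at the first scheduled value after rituximab ends. It is then dated at the first rise.
- Name the visit that supplies this value. The SPEP row of the calendar shows follow-up but no end-of-treatment entry, although a response assessment is scheduled then.
- Values taken after plasmapheresis or after new anti-lymphoma therapy may not be used to rule out PD.
- If no usable later value exists, the confirmed rise counts as PD.
- Report a sensitivity analysis that counts all confirmed rises.

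**Cost.** Protocol wording, record review for at most 24 patients, and one extra analysis. Follow-up SPEP is already in the calendar, so no new test is needed. The downside is that a real but temporary rise during rituximab is missed in the main analysis and appears only in the sensitivity analysis.

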1.0 OBJECTIVE

- 1.1 Primary Objective: Determine the overall response rate of single-agent weekly CFZ, measured after 2 cycles of therapy, in WM and MZL.
- 1.2 Secondary Objectives:
 - 1.2.1 Assess safety and tolerability of single agent, weekly CFZ in patients with WM and MZL, and determine the tolerability of weekly CFZ+rituximab for applicable patients.
 - 1.2.2 Estimate the time to best response, response duration, and survival with weekly CFZ for WM and MZL
 - 1.2.3 Evaluate the overall response rate associated with weekly CFZ in a subset of patients with rituximabrefractory WM or MZL

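### Kaplan-Meier for time to best response would overstate the proportion reaching best response if patients who die or are removed for progression before responding are censored; cumulative incidence avoids this

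*Combined protocol and SAP*

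**What the plan says.** Objective 1.2.2 is to "Estimate the time to best response, response duration, and survival with weekly CFZ for WM and MZL". The only analysis text for it is in 12.2: "Estimate time to best response, time to progression, and survival outcomes for subjects using Kaplan-Meier analysis". One method thus covers three kinds of endpoint. Section 12.2 also says: "Descriptive statistics will be used for baseline characteristics, and responses to treatment".

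Section 11.0 refers to diagnostic and response criteria. It does not say what event ends time to best response, who is analysed, or when a patient without a response is censored. Competing events are not mentioned anywhere.

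Four other provisions bear on who can leave before responding:

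- Section 7.1: "If protocol therapy is discontinued for disease progression requiring other treatment", then "patients may go on to receive other therapy at the discretion of their physician, but will be removed from this study".
- Section 7.3.1 lists symptomatic progression once at least four cycles have been given as a reason to stop protocol treatment. It adds that IgM flare after rituximab and "biochemical progression alone do not require removal from protocol treatment".
- Section 7.3.8: "The patient may withdraw from the treatment at any time for any reason". No analysis rule is attached.
- Section 7.2: patients without a response after cycle 2 continue with rituximab added, so they can still respond.

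Follow-up runs for one year from the start of drug (study calendar, note 8). Section 13.2 notes that the best paraprotein response can come months after therapy.

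**The concern.** Kaplan-Meier assumes that a censored patient has the same future chance of the event as those still under observation. A patient who has died, or who has been removed to start other treatment, can no longer reach a best response to protocol therapy. Censoring such a patient at exit redistributes that patient's weight to those who remain, some of whom will respond. The curve then estimates response in a setting where nobody dies or is removed, and it lies at or above the proportion of treated patients who actually reach best response.

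The endpoint adds a difficulty of its own. Best response is known only in retrospect, and patients who never respond have no event date, so how they enter the curve decides what the curve means.

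At stake is one secondary estimate: the curve and median reported for objective 1.2.2.

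**Working it through.** **The plan's own figures.** The documents state no figure for time to best response. The only design figures are those of the two-stage rule in 12.2 (9 then 24 patients, stop at 2 or fewer responses, reject at 10 or more). Summing P(X1 = x) × P(X2 ≥ 10 − x) over x = 3 to 9, with X1 binomial on 9 patients and X2 on 15, gives a type I error of 0.0485 at a 25% response rate and power of 0.8055 at 50%. These agree with the stated .05 and 80%. They use response counts after cycle 2, so nothing below changes them.

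**Inputs for the illustration (all assumed).** The documents give no rate of response over time, progression, death or removal. Assume a monthly hazard of best response r = 0.10, a monthly hazard of competing exit c = 0.02 or 0.04, and a 12-month horizon, which matches the one-year follow-up.

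**Case A: competing exits from month 0.**

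- 1 − Kaplan-Meier, with exits censored: 1 − exp(−12r) = 1 − exp(−1.2) = 69.9%.
- Cumulative incidence: r/(r + c) × [1 − exp(−12(r + c))].
  - c = 0.02: 0.8333 × [1 − exp(−1.44)] = 63.6%; excess 6.3 points.
  - c = 0.04: 0.7143 × [1 − exp(−1.68)] = 58.1%; excess 11.8 points.
- Share of patients with a competing exit, c/(r + c) × [1 − exp(−12(r + c))]: 12.7% and 23.2%.
- Median from Kaplan-Meier: ln 2/0.10 = 6.9 months. Cumulative incidence reaches 50% at −ln(0.4)/0.12 = 7.6 months and −ln(0.3)/0.14 = 8.6 months.

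**Case B: competing exits only after four 28-day cycles.** This follows the timing in 7.3.1. Four cycles are 112 days, or 3.68 months.

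- Response by 3.68 months: 1 − exp(−0.368) = 30.8%, leaving 69.2% at risk for a further 8.32 months.
- c = 0.02: 0.308 + 0.692 × 0.8333 × [1 − exp(−0.12 × 8.32)] = 67.2%; excess 2.7 points.
- c = 0.04: 0.308 + 0.692 × 0.7143 × [1 − exp(−0.14 × 8.32)] = 64.8%; excess 5.1 points.

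**Case C: hypothetical data on 24 patients.** Let 12 reach best response (6 at month 2, 2 at month 4, 3 at month 7, 1 at month 10). The true proportion is 50.0% throughout. Non-responder exits are censored when they occur.

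| Competing exits | 1 − Kaplan-Meier |
|---|---|
| None | 50.0% |
| 3 (one each at months 3, 5, 8) | 53.2% |
| 6 (two each at months 3, 5, 8) | 57.8% |
| 9 (three each at months 3, 5, 8) | 65.9% |
| 6, all after the last response | 50.0% |

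The six-exit row, for example, is 1 − (18/24)(14/16)(9/12)(6/7) = 57.8%.

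If only the 12 responders are analysed, nobody is censored and the curve reaches 100% by construction. There is then no bias, but the curve carries no information on the proportion responding.

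**The case against.** The strongest reply is that 12.2 does not say how exits will be handled. Keeping patients without a response in the risk set to the end of follow-up would remove the bias, and so would analysing responders only. That stands, and it is why the point is conditional. But the plan adopts neither option, and censoring at exit is what a reader would ordinarily understand by Kaplan-Meier.

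Three stronger readings are tempting, and the documents do not support them:

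- **Every progression or departure is a competing event.** Under 7.3.1, IgM flare or biochemical progression alone does not require removal, and under 7.2 initial non-responders continue with rituximab added. Withdrawal by choice (7.3.8) is ordinary censoring if it is unrelated to prognosis. The competing events are death and removal for progression or new therapy.
- **The excess will be 6 to 12 points.** That range needs the assumed hazards to run from month 0, whereas 7.3.1 places removal for symptomatic progression after at least four cycles. Deaths and removals under 7.1 could come sooner, so neither case is established. Section 2.1 describes these diseases as slow-moving, which makes high exit rates within a year less likely. With 24 patients the 95% half-width around 58% to 64% is about 19 to 20 points, so the bias would be smaller than the sampling error.
- **The trial's response rate will be inflated.** Section 12.2 summarises responses descriptively and tests the primary response rate as a proportion after two cycles. Nothing says that a response rate will be read from this curve.

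It is also fair to say that death before progression competes with time to progression. The recommendation to keep Kaplan-Meier is therefore limited to survival.

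**Conclusion.** The point holds in conditional form. If death and removal for progression or other treatment before response are treated as censoring, 1 minus Kaplan-Meier cannot fall below the cumulative incidence. It exceeds it whenever a best response occurs after such an exit, and the median is then read too early.

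The actual size cannot be computed from the documents. Under the assumed hazards the 12-month excess is about 6 to 12 points with exits from month 0, and about 3 to 5 points with exits starting after four cycles. The median shift in the month-0 case is 0.7 to 1.7 months (6.9 against 7.6 and 8.6). The excess is zero if all exits follow the last response or if only responders are analysed.

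Only secondary objective 1.2.2 is affected. The primary response rate, futility rule, type I error, power and sample size of 24 are unchanged. This is a free improvement, not a flaw in the design.

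**What to change.** In 12.2, take time to best response out of the Kaplan-Meier sentence and replace it with one of two options:

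- Estimate time to best response by cumulative incidence in all treated patients, with death and removal for progression or new therapy as competing events. State that IgM flare or biochemical progression alone is not a competing event, and that other loss to follow-up is censored.
- Summarise time to best response descriptively among responders (median and range), beside the response proportion with all treated patients as denominator. This fits the descriptive summary of responses that 12.2 already plans.

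Either way, define the event as the date on which the best response category is first documented. Keep Kaplan-Meier for survival.

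The cost is a sentence or two and standard software, with no extra patients. The only dates needed are those of response, removal, new therapy and death.
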